- The Investigator will obtain written informed consent/assent from potentially eligible subjects and/or legally acceptable guardian before any trial related procedure is performed. In case of extraordinary events (e.g., COVID-19 pandemic) it is acceptable to have the informed consent via e-mail, SMS or a verbal consent (a witness is required) if allowed per local country guidance. Written consent has to be provided as soon as possible and must be properly recorded in the source documentation.

- As of the date of informed consent for each subject, the sites will document
 in the electronic Case Report Form (eCRF) all AEs and changes/additions
 made to concomitant medications. SAEs will be reported as they occur but
 no later than 24 hours after the Investigator's awareness of the event.
- Subject demographics and baseline characteristics will be assessed according to Table 1, including medical/medication history, physical examination, vital signs, weight and height.
- A single 12-lead ECG will be conducted, and the ECG print-out will be filed.
- A blood test will be drawn, which will be analysed centrally, to determine if the subject is eligible according to the main inclusion and exclusion criteria. The main assays to be performed in order to assess eligibility are: Hb, serum ferritin. In addition, other clinical biochemistry, haematology, clotting parameters will be taken from the same blood draw. Date and time of blood draw will be documented in the eCRF. In addition the results from urinalysis parameters and urine drug and alcohol screen will be assessed locally and reported in the eCRF.
- During the same blood draw, a serum pregnancy test will be taken for females of childbearing potential.
- A serology test will be conducted to determine HBsAg, HBV, HCV, HIV.

Screening Visit V2 (Day -15±3 Days, Optional)

Screening Visit V2 – performed in-hospital (optional):

- If a subject did fulfil the main inclusion criteria and did not meet exclusion criteria observed from the Visit V1, they may be asked to attend a second screening Visit V2 in order to determine the Hb level. If for logistical reasons the subject may not be able to attend the Visit V2, the V1 screening Hb value in conjunction with a historical Hb value obtained at maximum 2 weeks prior to screening (Day -28), or an additional Hb value taken prior to randomisation can be assessed.

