8.1.9 Local Laboratory Parameters

The laboratory tests to be assessed and analysed locally according to Table 1 results will be transferred into the eCRF.

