8.1.10 Central Laboratory Parameters

Details concerning the central blood samples collection, blood withdrawal, processing and storage will be provided in a Laboratory instruction manual. The following Laboratory parameters will be assessed during the study according to Table 1.

Although the assessments should preferably be performed centrally, due to COVID-19 pandemic, assessment may be performed in a local laboratory at site or at a laboratory near to subject's home in case shipment of samples to the central laboratory is no longer

possible. This would notably concern key safety laboratory parameters which should at minimum include haematology panel (RBC, Hb, haematocrit, mean corpuscular volume, mean corpuscular Hb, mean corpuscular Hb concentration, white blood cell count with differential, platelets count), coagulation (prothrombin time, activated partial thromboplastin time, thrombin time) and liver function tests (ALT, AST, GGT total bilirubin, alkaline phosphatase).

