12.8 Safety Evaluations

12.8.1 Primary

All safety analyses will be performed on the SS.

If at least 1 subject is randomised in each body weight category, all safety tabulations will be repeated by body weight category.

Adverse Events

Only TEAEs defined as events with an onset date later or on the same date as first study drug intake will be tabulated. AEs that occurred during the study but before first study drug intake will be only listed.

A summary table with the counts and percentage of subjects and the number of events will be provided on overall subjects receiving VIT-2763, subjects receiving VIT-2763 by dose daily frequency and on all subjects receiving placebo within each cohort, for any TEAEs, any severe TEAEs, any serious TEAEs, any TEAEs leading to study withdrawal, any TEAEs leading to death.

All AEs will be coded according to a standard dictionary (MedDRA).

Tables of the counts and percentages of subjects with at least 1 TEAE by SOC and PT will be provided for all TEAEs and TEAEs by severity and by relationship to study drug on overall subjects receiving VIT-2763, subjects receiving VIT-2763 by dose daily frequency and on all subjects receiving placebo within each cohort.

Same tables according to SOC and PT will be provided for serious TEAEs, TEAEs leading to premature discontinuation of the study and TEAEs leading to death.

Clinical Laboratory Tests

Values by visit from baseline and changes from baseline by post-baseline visit for the haematologic, biochemistry and urinalysis parameters will be summarised on overall subjects receiving VIT-2763, subjects receiving VIT-2763 by dose daily frequency and on all subjects receiving placebo.

Shift tables crossing counts of baseline values lower, within and higher than laboratory normal range with the counts of each post-baseline visit will be provided for the haematologic, biochemistry and urinallysis parameters on the same treatment groups.

Vital Signs and Body Weight

Values by visit from baseline and changes from baseline by post-baseline visit for blood pressure, pulse rate and body weight will be summarised on overall subjects receiving VIT-2763, subjects receiving VIT-2763 by dose daily frequency and on all subjects receiving placebo.

ECGs

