### 2.6 Study Endpoints

### 2.6.1 Primary Safety Endpoint(s)

[figure not shown]
- Reported or observed adverse events (AEs): by system organ class (SOC) and preferred term (PT) (MedDRA coded term), by severity and relation to study product in each treatment group.
- Reported or observed serious AEs (SAEs): by SOC and PT (MedDRA coded term), by severity and relation to study product in each treatment group.
- Changes in vital signs (supine systolic and diastolic blood pressure and pulse rate), clinical laboratory safety tests (haematology, serum biochemistry, coagulation, and urinalysis), 12-lead ECG, and physical examination findings.

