### 5.7.2 Clinical Laboratory Evaluations

A list of all protocol specified clinical laboratory tests are given in Appendix A and will be performed at screening, baseline, week 1, week 2, week 4, week 8 and week 12 for haematology, biochemistry and urinalysis and at screening, baseline, week 4 and week 12 for coagulation in accordance with the Schedule of Events in section 2.3. For analyses, Planned Assessment Windows (see Section 2.2.3) are defined for each visit.

Descriptive statistics will be performed for laboratory parameters on a continuous scale for the scores and change from baseline for each visit split by treatment group.

If multiple tests were performed at baseline, the latest non-missing measurement prior to the first administration of study treatment will be used for the baseline value. For multiple tests at post-baseline visits occurring during the same visit window, the closest measurement will be used for the analyses and summary tables. When two measurements are exactly equidistant to the exact visit date, the later will be used for the analyses and summary tables. Laboratory values expressed as 'less than" or "greater than" will be imputed using the next numerical value (i.e. '<2.00' imputed as 1.99, ">0.3" imputed as 0.4).

Shift tables for the haematology and biochemistry laboratory parameters comparing values low, normal and high using the standard reference ranges will be presented for the baseline laboratory measurement versus the endpoint measurement for each subject. The number and percentage of subjects with abnormal values for each analyte will be summarized at each analysis visit. Abnormal values for each analyte will be determined using normal ranges provided by the central laboratory. The descriptive analysis by visit will also include an overall summary. If any of the subject's post-baseline measurements are abnormal (low or high), then the subject is classified as abnormal in the overall summary.

All laboratory results (local and central values) will be listed, including all unscheduled visits.

Only central laboratory parameters will be analysed.

eGFR formula: 186 x (Creatinine/88.4)-1.154 x (Age)-0.203 x (0.742 if female) x (1.210 if black)

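### Locally assessed urinalysis, part of the primary safety endpoint, would be listed but not summarised by arm under SAP 5.7.2, and its protocol-planned shift tables are dropped without being declared

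*SAP*

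**What the plan says.** **Endpoint.** SAP 2.6.1 counts changes in "clinical laboratory safety tests (haematology, serum biochemistry, coagulation, and urinalysis" among the primary safety endpoints. Protocol 3.4.1 does the same.

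**Protocol analysis plan.** Section 12.8.1 says that values by visit and changes from baseline for the "haematologic, biochemistry and urinalysis parameters will be summarised on overall subjects receiving" VIT-2763, by dose frequency, and on placebo. Its next paragraph adds shift tables against the laboratory normal range at each post-baseline visit, again naming urinalysis.

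**Where urine is tested.** For screening visit V1 the protocol synopsis says that "the results from urinalysis parameters and urine drug and alcohol screen will be assessed locally and reported in the eCRF". Section 8.1.9, which covers local tests, states "The laboratory tests to be assessed and analysed locally according to Table 1 results will be transferred into the eCRF"; urinalysis sits beneath it in 8.1.9.2, with a parenthesis that permits central assessment. For remote or home visits, section 9.1.4 asks for local processing of urine.

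**SAP 5.7.2.** It says "A list of all protocol specified clinical laboratory tests are given in" Appendix A and names urinalysis in the visit schedule that follows. Shift tables are planned for haematology and biochemistry. All results, local and central, are to be listed, but "Only central laboratory parameters will be analysed".

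**Precedence.** SAP section 1 gives the SAP priority where the two documents differ. SAP 1.2, on changes from the protocol, records only the modified FAS.

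**The concern.** The protocol routes urinalysis to local laboratories by default, and the SAP analyses only central results. Each rule is reasonable alone. Together they remove from the by-arm tables a component that both documents place in the primary endpoint.

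This trial has no inferential comparison (Protocol 12.1, SAP 3.2), so descriptive tables by arm are the planned means of comparing active treatment with placebo. A subject-level listing does not do that job. The protocol itself treats urine findings as relevant to safety: albuminuria is part of exclusion criterion 8, and urine protein, glucose and blood are graded in the toxicity scale of Protocol Appendix 2. Because the SAP prevails and SAP 1.2 is silent, a programmer following the SAP would have no instruction to produce the tables, and a reader of the report would not be told that they had been dropped.

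**Working it through.** No sample size, power or alpha figure is involved, and the plan gives no figure of its own to reproduce. The check is a comparison of text plus simple counts.

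**1. Contents of Appendix A as shown.** Haematology 12 rows, biochemistry 32, coagulation 3: 12 + 32 + 3 = 47. The protocol's urinalysis has seven items: pH, four dipstick items (blood, glucose, ketone, protein) and two spot-urine ratios (protein/creatinine, albumin/creatinine). Items found in Appendix A: 0 of 7.

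**2. What each panel receives.**

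| Panel | Listed | By-visit summary by arm | Shift table |
|---|---|---|---|
| Protocol 12.8.1, any laboratory | – | yes | yes |
| SAP 5.7.2, run locally | yes | no (central-only rule) | no (haematology and biochemistry only) |
| SAP 5.7.2, run centrally | yes | possible under the general wording, but no Appendix A row | no (same restriction) |

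The missing shift table therefore does not depend on where the sample was run. The missing by-visit summary does. If only some sites used central assessment, the central-only rule would tabulate a subset selected by site.

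**3. Fit of the method.** SAP 5.7.2 plans descriptive statistics on a continuous scale and defines abnormality by the central laboratory's ranges. Dipstick results are categories, and local results do not come with central ranges. SAP 5.1.1 has standard categorical statistics that would serve, but 5.7.2 does not apply them to urinalysis.

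**4. Size.** The schedule of events has nine visits. Urinalysis is not done at V2 or V9, so 9 − 2 = 7 panels per subject (V1, V3–V8). Removing V1 and V3 leaves 7 − 2 = 5 post-baseline panels (V4–V8).

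- All scheduled panels, 36 randomised subjects: 7 × 36 = 252.
- Post-baseline panels, 36 subjects: 5 × 36 = 180.
- Post-baseline panels from 30 completers alone: 5 × 30 = 150.

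The documents do not give the share *f* of panels run locally, so I treat it as an assumption. Post-baseline panels without a by-visit summary number *f* × 180: 180 if *f* = 1, 90 if *f* = 0.5, 0 if *f* = 0. The shift tables are lost at every value of *f*.

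**The case against.** **Central assessment is allowed.** The V1 text covers screening only, the local-processing instruction in Protocol 9.1.4 covers remote visits, and 8.1.9.2 permits central assessment. A reader might infer that urinalysis is local by design at every visit. The documents do not support that: local is the default, and it is unclear whether the permission covers the whole urinalysis line or only the spot-urine ratios. This limits the size of the by-visit gap. It does not restore the shift tables.

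**The appendix may be incomplete here.** SAP footers count 64 pages, and the visible text ends with the coagulation table. A urinalysis table may have been lost in extraction. That stands, so the missing rows are supporting evidence only. The central-only sentence and the shift-table restriction are both in 5.7.2 itself and conflict with Protocol 12.8.1 whatever Appendix A contains.

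**Other safety outputs remain.** A reader might infer that a renal signal would go unseen. That is too strong. Creatinine, urea nitrogen, eGFR, albumin and total protein are in Appendix A and are tabulated; a laboratory change judged clinically significant is recorded as an AE (Protocol 10.5.4), and treatment-emergent AEs are tabulated by arm. What is lost is the by-arm view of urine findings that do not become AEs.

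**The white cell differential.** Appendix A shows total WBC only, and a reader might infer that the differential goes untabulated. The documents do not establish this. Scheduled haematology is central, so the central-only rule does not exclude it, and no SAP sentence limits tables to Appendix A rows. The phrase "white blood cell count with differential" in Protocol 8.1.10 comes from a minimum panel for COVID-19 local testing; the routine haematology analyte list is not visible. This is an ambiguity to clarify, no more.

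**Conclusion.** The concern holds for urinalysis. As written, SAP 5.7.2 leaves locally assessed urinalysis in listings only and plans no urinalysis shift table, contrary to Protocol 12.8.1 and without an entry in SAP 1.2. Up to seven scheduled panels per subject are involved, five of them post-baseline. The shift-table loss is complete; the by-visit loss is proportional to the share of panels run locally, which the documents do not state.

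The conclusion rests on reading the central-only sentence literally and on 8.1.9 setting local assessment as the default. It does not rest on Appendix A being complete as shown. In a small descriptive trial with full listings, retained renal chemistry and AE tables, this is a correction that should be made, but it does not by itself undermine the safety evaluation.

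**What to change.** In SAP 5.7.2:

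- Exempt urinalysis from the central-only rule, for example: *urinalysis is analysed from all available results, local or central*. Naming only local results would leave out panels run centrally, which the protocol permits.
- Restore the by-visit summaries and shift tables of Protocol 12.8.1 for urinalysis: counts by category for the dipstick items, continuous summaries for pH and the two spot-urine ratios after units are harmonised. State which reference range applies to local results.
- Add the seven urine parameters to Appendix A.

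If the sponsor prefers to keep urinalysis in listings only, SAP 1.2 should declare and justify that departure.

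As a secondary clarification, state whether the centrally measured white cell differential is tabulated, and add its rows to Appendix A if so.

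The cost is SAP wording, a few extra tables from data already collected, and possible unit harmonisation across local laboratories. No visit, sample or protocol procedure changes.

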5.2 Inclusion Criteria

The following inclusion criteria must be met for each subject:

- 1. Documented diagnosis of NTDT, including a β -thalassaemia intermedia-phenotype.
- 2. NTDT is defined as subjects having received <5 units of red blood cells (RBCs) during the 24-week period prior to randomisation/first drug administration of VIT-2763 or placebo (Day 1; 1 unit is defined as 200 to 350 ml of transfused packed RBCs and last RBC transfusion must have been received ≥14 days prior to randomisation).
 - Note: Subjects who are supposed to receive RBC transfusions after randomisation in the Investigator's opinion, and according to local practise, and having received at least 1 dose of VIT-2763, may be considered to stay on study treatment for safety reasons, and in case there are no tolerability concerns. Subjects will be censored for secondary efficacy.
- 3. Male and female adult* NTDT subjects, 18-65 years of age inclusive (Cohort I only) at time of screening.

- * Following section in italics is applicable for dedicated Thailand site(s) as per local EC/IRB guidance:
- 3. Male and female adult NTDT subjects, 20-65 years of age inclusive (Cohort I only) at time of screening.
- 4. Male and female adolescent* NTDT subjects, 12-17 years of age inclusive (Cohort II only) at time of screening.
- * Following section in italics is applicable for dedicated Thailand sites(s) as per local EC/IRB guidance:
- 4. Male and female adolescent NTDT subjects, 12-19 years of age inclusive (Cohort II only) at time of screening.
- 5. Subjects must have a mean baseline Hb \leq 11 g/dl, based on at least 2 consecutive measurements \geq 1 week apart within 6 weeks prior to randomisation/baseline.
 - Note: If obtained Hb values show more than 10% relative difference and more than 1.0 g/dl absolute change between the highest and lowest value, the subject must be excluded. If there is 1 retrospective Hb value available for the subject at maximum of 2 weeks prior to screening (Day -28), the Hb value can be taken into consideration. A subject not meeting this criterion would be excluded but can be rescreened at maximum 2 times at a later time point.
- 6. Ability to understand the requirements of the study and abide by the study restrictions, and agreement to return for the required assessments.
- 7. Ability to swallow a capsule Size 0, to be assessed during the screening visit.

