5.3 Exclusion Criteria

Note: Assessment of laboratory parameters and other baseline exclusionary characteristics apply at screening Visit V1, if not indicated otherwise.

The following criteria exclude a subject from participating in this trial:

- 1. Documented diagnosis of TDT, including a beta-thalassaemia major phenotype (including $\beta 0/\beta 0$, $\beta +/\beta +$, $\beta 0/\beta +$ genotype), and mixed compound heterozygous for sickling phenotype variants such as Hb S/ β -thalassaemia, or transfusion dependent non-deletional Hb H disease (i.e., Hb constant spring) or Hb C disease.
- 2. Subjects on concomitant ICT or subjects on prior ICT which was discontinued less than 4 weeks prior randomisation. If ICT was discontinued >4 weeks prior randomisation the subject is eligible.
- 3. Subjects with either serum ferritin <150 ng/ml or a documented LIC ≤1.5 mg/g liver dry weight assessed through MRI.

Note: If documented LIC MRI scans retrieved within 24 months prior to randomisation are not available per local practice, serum ferritin will be used only to document iron overload status.

- 4. Subjects with TSAT <30%.
- 5. Subjects with documented LIC >15 mg/g liver dry weight assessed through MRI, or a documented myocardial T2* <20 ms, if available per local practice and retrieved within 24 months prior to randomisation.
- 6. Adult or adolescent subjects with body weight <40.0 kg or >100 kg at screening.

- 7. Chronic liver disease and/or ALT, AST or GGT above 3-fold the ULN range at screening.
 - Note: A subject fulfilling this criterion will be excluded but can be rescreened at a later time point (in order to fulfil eligibility, ≥ 2 values within ≥ 1 week should be assessed and be within eligibility limits).
- 8. eGFR <30 ml/min/1.73 m² (according to chronic kidney disease classification Stage 4 or higher), and/or significant albuminuria >30 mg/mmol. eGFR should be estimated according to Chronic Kidney Disease Epidemiology Collaboration formula (CKI-EPI) in adults, and Schwartz formula in adolescents.
- 9. Newly diagnosed folate deficiency anaemia and/or Vitamin B_{12} megaloblastic anaemia. Subjects with known folate deficiency anaemia and/or Vitamin B_{12} megaloblastic anaemia who are on ≥ 12 weeks stable replacement therapy are eligible.
 - Note: A subject fulfilling this criterion will be excluded but can be rescreened at a later time point.

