8.1.10.1 Haematology, Biochemistry, Blood Clotting and Serology

- Electrolyte status (sodium, potassium, magnesium, calcium, chloride), total bilirubin, urea, uric acid, creatinine, total protein, alkaline phosphatase, AST, ALT, GGT, glutamate dehydrogenase, LDH, haptoglobin, amylase, bicarbonate, eGFR, unconjugated bilirubin, creatine phosphokinase, folic acid, Vitamin B₁₂, albumin, glucose, total cholesterol, and triglycerides. Total serum iron, serum ferritin, unsaturated iron binding capacity, calculated TSAT (screening visit only).
- Prothrombin time, activated partial thromboplastin time, thrombin time.
- Beta-human chorionic gonadotropin in serum.
- HIV 1/2 antibodies, HCV antibodies and RNA, HBsAg, hepatitis B core antibodies and optional HBV DNA.

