12.12 Other Evaluations

12.12.1

Values by visit from baseline and changes from baseline by post-baseline visit for Hb, reticulocytes, amylase, bicarbonate, eGFR, will be summarised on overall subjects receiving VIT-2763, subjects receiving VIT-2763 by dose daily frequency and on all subjects receiving placebo.

The counts and percentages of subjects achieving an increase in Hb \geq 1.0 g/dl and the ones achieving an increase in Hb \geq 1.5 g/dl will be provided by visit on the same treatment groups.

If at least 1 subject is randomised in each body weight category, the summary statistics will be repeated by body weight category.

Analyses will be performed on the FAS and the PPS. In case both analysis sets are identical, analysis will not be repeated.

Values by visit from baseline and changes from baseline by post-baseline visit for will be summarised on overall subjects receiving VIT-2763, on subjects receiving VIT-2763 by dose daily frequency and on all subjects receiving placebo.

Analyses will be performed on the FAS and the PPS. In case both analysis sets are identical, analysis will not be repeated.

If at least 1 subject is randomised in each body weight category, the summary statistics will be repeated by body weight category.

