### 5.1 General Considerations

The software used for all summary statistics and statistical analyses will be SAS® Version 9.4 or later (SAS Institute, Inc.).

Derived datasets will be generated by the Biostatistics Department from the Clinical Interchange Standard Consortium (CDISC) Study Data Tabulation Model (SDTM [version 3.2]) datasets in accordance with CDISC ADaM version 2.1 and the ADaM Implementation Guide v1.1.

The two cohorts (adults/adolescents) will be analysed the same way into 2 separated analyses, if 5 or more adolescents are randomised into the study. Otherwise, a pooled analysis of adult and adolescent subjects will be performed.

The treatment groups will be displayed as:

- 1. VIT-2763 QD
- 2. VIT-2763 BID
- Placebo

If at least 1 subject is randomised in each body weight category, summary statistics will be repeated in each body weight category.

There is no formal statistical level for this study, and all analyses are considered descriptive.

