# **Biochemistry parameters:**

Test Description	Conventional Units	SI Units	Number of decimal places
Serum Sodium	mEq/L	mmol/L	0
Serum Potassium	mEq/L	mmol/L	1
Magnesium	mg/dL	mmol/L	1
Calcium (EDTA)	mg/dL	mmol/L	1
Serum Chloride	mEq/L	mmol/L	0
Total Bilirubin	mg/dL	umol/L	1
Urea Nitrogen	mg/dL	mmol/L	0
Serum Uric Acid	mg/dL	umol/L	1
Creatinine(Rate Blanked)-2dp	mg/dL	umol/L	2
Total Protein	g/dL	g/L	1
Alkaline Phosphatase	U/L	U/L	0
AST (SGOT)	U/L	U/L	0
ALT (SGPT)	U/L	U/L	0
GGT	U/L	U/L	0
Glutamate Dehydrogenase-RUO	U/L	U/L	0
LDH	U/L	U/L	0
Haptoglobin	mg/dL	g/L	0
Serum Amylase	U/L	U/L	0
Serum Bicarbonate	mEq/L	mmol/L	1
eGFR (CKD-EPI GFR)	mL/min/1.73m 	mL/min/1.73m 	0
Unconjugated bilirubin (indirect bilirubin)	mg/dL	umol/L	0
Creatine Kinase	U/L	U/L	0
Folic acid (folate)	ng/mL	nmol/L	1
Vitamin B12	pg/mL	pmol/L	0
Albumin-BCG	g/dL	g/L	1

Serum Glucose	mg/dL	mmol/L	0
Cholesterol (High Performance)	mg/dL	mmol/L	0
Triglycerides (GPO)	mg/dL	mmol/L	0
Total Iron, Serum	ug/dL	umol/L	0
Ferritin	ng/mL	ug/L	1
Unsaturated Iron Binding Capacity	ug/dL	umol/L	0
Transferrin-CL	mg/dL	g/L	3

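### SAP 5.7.2 prints one eGFR equation for everyone, SAP Appendix A names CKD-EPI, and neither gives adolescents the Schwartz value used for their eligibility

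*SAP*

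**What the plan says.** SAP 5.7.2 (Clinical Laboratory Evaluations) prints "eGFR formula: 186 x (Creatinine/88.4)-1.154 x (Age)-0.203 x (0.742 if female) x (1.210 if black"). It applies to every subject and uses only creatinine, age, sex and race. The same section refers to Appendix A for the list of laboratory tests and states "Only central laboratory parameters will be analysed".

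SAP Appendix A, under the biochemistry parameters, has one eGFR row, labelled "eGFR (CKD-EPI GFR"). There is no paediatric row.

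Protocol 5.3, exclusion criterion 8, sets the eligibility method: CKD-EPI in adults "and Schwartz formula in adolescents".

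eGFR is also an analysed parameter. Protocol 8.1.10.1 puts it in the central biochemistry list ("amylase, bicarbonate, eGFR, unconjugated bilirubin"), and protocol 12.12 summarises it by visit with change from baseline ("Hb, reticulocytes, amylase, bicarbonate, eGFR"). Neither place names a formula.

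SAP 5.1 analyses the cohorts separately if at least 5 adolescents are randomised. "Otherwise, a pooled analysis of adult and adolescent subjects will be performed". At Thai sites, protocol 5.2 places 18- and 19-year-olds in the adolescent cohort: "Male and female adolescent NTDT subjects, 12-19 years of age inclusive (Cohort II only) at time of screening".

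**The concern.** The printed equation has the MDRD form: one power of creatinine, one power of age, and multipliers for sex and race. That is not CKD-EPI, so the SAP names two methods for one parameter. The precedence clause in SAP section 1 ranks the SAP above the protocol, but it cannot settle a conflict between two parts of the SAP. SAP 1.2 (Changes from Protocol) mentions no change to eGFR.

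For adolescents the gap follows from the text alone. A single equation with no height and no age split cannot be both the adult and the adolescent method that the protocol uses at screening. If the cohorts are pooled, one eGFR summary would cover both age groups.

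Serum biochemistry is part of the primary safety endpoint, and 5.7.2 asks for visit summaries, change from baseline, shift tables and counts of abnormal values. If the 5.7.2 equation is used, the tabulated eGFR cannot be compared with the eGFR on which subjects were admitted.

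**Working it through.** The plan states no eGFR value, so there is no figure to reproduce. The check is how far apart the candidate methods lie.

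**Inputs from the documents.** The SAP 5.7.2 equation, with −1.154 and −0.203 read as exponents (the lost superscripts are a text-extraction effect). Adult ages 18–65. Adolescent ages 12–17, or 12–19 at Thai sites.

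**Assumed inputs, absent from the documents.** Creatinine (Cr) values and heights, plus standard coefficients, with s = Cr/88.4 and Cr in µmol/L. No race factor is applied.

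- CKD-EPI 2009: 141 × min(s/κ,1)^α × max(s/κ,1)^−1.209 × 0.993^age × 1.018 if female; κ = 0.9 (male) or 0.7 (female); α = −0.411 or −0.329.
- CKD-EPI 2021: 142 × min(s/κ,1)^α × max(s/κ,1)^−1.200 × 0.9938^age × 1.012 if female; same κ; α = −0.302 or −0.241.
- Schwartz: k × height (cm) / s, with k = 0.413 to 0.55.

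**Worked adult example.** For a man aged 30 with creatinine 40 µmol/L, the SAP equation gives 186 × (40/88.4)^−1.154 × 30^−0.203 = 186 × 2.497 × 0.501 = 233. CKD-EPI gives 145 to 152.

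| Age 30 | Cr (µmol/L) | SAP 5.7.2 | CKD-EPI (2009 and 2021) |
|---|---|---|---|
| Man | 40 | 233 | 145–152 |
| Man | 70 | 122 | 120–122 |
| Man | 80 | 105 | 113–117 |
| Man | 100 | 81 | 87–90 |
| Woman | 40 | 173 | 132–134 |
| Woman | 60 | 108 | 117–120 |

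Units are ml/min/1.73 m². Over ages 18, 30, 50 and 65, both sexes and creatinine 40–100, the ratio of SAP to CKD-EPI runs from 0.88 to 1.71.

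**Change from baseline, man aged 30.**

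- Creatinine 40 to 50: −53 by the SAP equation, −10 to −13 by CKD-EPI.
- Creatinine 80 to 100: −24 by the SAP equation, −27 to −28 by CKD-EPI.

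**Worked adolescent example.** For a boy aged 14, 155 cm, creatinine 50 µmol/L, the SAP equation gives 186 × (50/88.4)^−1.154 × 14^−0.203 = 186 × 1.930 × 0.585 = 210. Schwartz gives 0.413 × 155/(50/88.4) = 113, or 151 with k = 0.55.

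Over ages 12, 14, 17 and 19, heights 140–170 cm, creatinine 30–80 and both sexes, the ratio of SAP to Schwartz is 1.10–2.29 with k = 0.413 and 0.82–1.72 with k = 0.55.

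**Height, for any k.** Two adolescents of the same age, sex and creatinine at 140 and 170 cm get the same SAP value, but Schwartz values in the ratio 170/140 = 1.21, a difference of 21%.

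**The case against.** The strongest reply has four parts.

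1. **Redaction.** Protocol 12.12, which summarises eGFR, probably corresponds to SAP 5.6.3, and the content of that section is blacked out. The hidden text might name the eGFR source. This does not rescue the plan: 5.7.2 is legible, summarises the Appendix A biochemistry parameters itself, and still conflicts with Appendix A.

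2. **Schwartz is required for eligibility only.** No visible passage says the analysis eGFR must match the eligibility eGFR, so leaving Schwartz out of the SAP breaks no explicit rule. That is correct. The adolescent point is that the plan uses one method to admit subjects and another to describe them, without saying so.

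3. **The large ratios are grid corners.** The 1.71 belongs to a 65-year-old man at 40 µmol/L. At 60 µmol/L and above the adult ratio is 0.88 to 1.24. At 200 µmol/L, with eGFR near the exclusion limit of 30, the adult equations differ by less than 3 at ages 20–50. Height cancels from within-subject proportional change: a 25% rise in creatinine gives −22.7% by the SAP equation and −20.0% by Schwartz. All of this stands, and it confines the problem mainly to absolute values at low creatinine and in adolescents.

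4. **Little depends on it.** Nothing is tested, no visible stopping rule uses eGFR, and one equation in all arms favours none. This also stands. It limits the seriousness but does not tell a programmer which value to tabulate.

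Reading the central-laboratory sentence as choosing the laboratory's CKD-EPI value is possible, but then the printed equation has no purpose.

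**Conclusion.** The concern holds. SAP 5.7.2 and Appendix A specify different eGFR methods, nothing visible ranks one above the other, and neither supplies the Schwartz value used for adolescent eligibility. The contradiction and the adult/adolescent gap rest on the documents; identifying the printed equation as not CKD-EPI rests on the standard forms of the named methods.

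The numerical size is illustrative and depends on the assumed coefficients, creatinine values and heights. Under those assumptions the choice of method can change a tabulated adult value by up to 71% and can more than double an adolescent value, while near 70 µmol/L in a man aged 30 it makes almost no difference. It should be corrected before the tables are programmed. It does not threaten the trial's main conclusions.

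**What to change.** Remove the equation from SAP 5.7.2. Tabulate the central-laboratory CKD-EPI eGFR for adults and a Schwartz eGFR for adolescents, the latter from central creatinine and screening height with k stated, and amend Appendix A to match. State whether the adolescent method follows cohort or age, because 18- and 19-year-olds at Thai sites belong to Cohort II. If the cohorts are pooled, show eGFR separately for adults and adolescents.

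If the sponsor intends an equation other than the eligibility one, state it once, use the same label in 5.7.2 and Appendix A, and declare it in SAP 1.2.

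The cost is SAP wording and one extra derivation. No new data are needed: biochemistry, including creatinine, is scheduled at screening and at visits 3 to 8. Height is measured at screening only (protocol 8.1.5), so the Schwartz value would use a fixed height throughout.
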